Aim: To test the proof of principal that JNJ-39393406 promotes smoking cessation. We have developed, tested, and validated an innovative and efficient Phase 2a screening procedure that optimally combines the validity of randomized clinical trials with the practicality of lab- based medication studies. As detailed elsewhere (Perkins & Lerman 2014), it employs a within-subject, cross-over design comparing active versus placebo effects on quitting smoking to maximize statistical power without a large sample. We have demonstrated the sensitivity of this approach in identifying efficacy for biochemically-verified (CO) abstinence in all 3 of the first- line FDA-approved cessation medications, as well as its specificity in identifying lack of efficacy for abstinence in a medication known to not aid cessation. Using this procedure, we will evaluate effects of JNJ-39393406 vs. placebo on short-term smoking abstinence in smokers who already have a high interest

in quitting soon. We predict that, compared with placebo, JNJ-39393406 will increase days of abstinence, identifying initial evidence of efficacy for smoking cessation.

Our main dependent measure is days of very stringent biochemically validated (expired CO<5 ppm) 24-hr smoking abstinence, with post-quit withdrawal and cognitive function as secondary measures. Potential for adverse side-effects will be assessed at each visit. We hypothesize that the number of days of abstinence will be significantly greater for JNJ-39393406 vs. placebo.

Study Design and Methods

Random assignment: Upon entry into the study, subjects will be randomly assigned in double-blind fashion to medication order (active drug then placebo, or vice versa) within the cross-over design. We will use permuted-block randomization to assign subjects to these medication order conditions. The same order assignment will not be repeated more than 3 consecutive times, to prevent an imbalance in the sequence of these orders.

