Medication: Active JNJ-39393406 (50 mg tablets), abbreviated here “JNJ” (IND #122957) and matching placebo (both from Janssen Research and Development LLC) will be encapsulated by the WPIC Investigational Drug Service (IDS) research pharmacy. Staff and participants are blind to medication assignment by IDS (i.e. double blind). To start the dose run-up, participants will take one capsule of JNJ-39393406 (50 mg), or identically appearing placebo, once on day 1, incrementing by 50 mg daily to reach 200 mg by day 4. The full dose involves two capsules, each twice per day (100 mg b.i.d. for JNJ), in the a.m. and evening, over the remaining 7 days of that medication condition, including the 5-day practice quit period (Mon-Fri), when they will come to the lab each day to provide CO validation of quit status, plus provide self-reported withdrawal and possible adverse effects. One day will also include computerized test of cognitive processing (see below). One week of *ad lib* smoking follows the first quit attempt phase prior to the dose run-up week with the other condition, to allow separate 3-week tests of each in aiding smoking abstinence.

Procedure: Participation for each subject will be 6 weeks after randomization, involving two 3-week phases, one for each drug condition in this double-blind, crossover procedure. For each phase, visits occur on Mon and on Thurs of the first 2 weeks and Mon-Fri of the third week. CO is assessed upon arrival to each session, along with MNWS withdrawal. Each phase begins with a week of *ad libitum* smoking (baseline, week 1), with drug regimen started on Mon a.m. of week 2 while continuing to smoke (dose run-up). On week 3, they are instructed to try to abstain as of Sun am through the mid-day Fri visit, with CO assessments of quit status on Mon-Fri of week 3. On Mon of week 3, all completed testing of cognitive function (CPT). After Fri of week 3, all then *ad lib* smoke for at least a week to repeat this 3-week phase for the other condition: smoking without drug (i.e. washout; week 4), next dose run-up (week 5), and trying to quit during Mon-Fri (week 6).

Measures:

Smoking outcome. During the “quit week” (week 3) of each condition, the primary outcome of 24-hr abstinence is assessed daily on Mon-Fri by expired-air carbon monoxide (CO) <5 ppm.

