Secondary outcomes. Also examined daily are abstinence symptoms on the Minnesota Nicotine Withdrawal Scale (MNWS) (Hughes *et al.* 1991), with each item scored on a 0-100 VAS. In addition, we will assess the Penn Continuous Performance Task (CPT) assessing sustained attention (Kurtz *et al.*, 2001; Gur *et al.*, 2010) on Mon of each quit week. Also assessed daily (Mon-Fri) of the two “quit” weeks (weeks 3 and 6) are medication blinding and side-effects, rated on a 0 to 3 scale (none, mild, moderate, severe). Potential adverse effects will also be assessed by repeat of EKG and lab tests (see end of screening in Eligibility section below) on Fri of week 3 on each condition.

Eligibility Criteria

Randomized will be 60 dependent smokers aged ≥ 18 and < 66 (about 30 women, 30 men) with a high interest in quitting smoking (defined below), i.e. those shown in our prior research to be more sensitive to cessation medication efficacy. All subjects will be smokers with a high interest in quitting soon (within 3 months). Subjects also will be those who have smoked at least 10 cigarettes per day for at least 1 year, with no current use of non-tobacco nicotine products. To obtain 60 participants, we expect to screen about 80 male or female smokers, aged ≥ 18 and < 66 years, living in Allegheny or neighboring counties of the greater Pittsburgh metropolitan region, who do not have significant health problems. We will also assess the Fagerstrom Test of Nicotine Dependence (FTND; Heatherton *et al.* 1991) and other smoking characteristics, but will not select based on these factors. We selected these inclusion criteria because they approximately fit the current FDA-approved indications for smoking-cessation medications, and because we are interested in responses to this active compound, JNJ-39393406, among dependent smokers with an interest in quitting, those most likely to use such medications to help them quit smoking.

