Screening will also include assessment of alcohol use via the AUDIT (Saunders *et al.* 1993), as those with scores indicating dependence are excluded. Self-report of no more than 15 drinks/week and 3 drinks on any day in the past week are required. Those not ineligible at screening will receive a physical exam by study physician, including EKG, bloodwork to check liver and kidney function (CBC, etc.), illicit drug screen (other than THC), urine pregnancy test (women), and interview to assess history of psychiatric disorders, suicidal ideation, current major health problems (e.g. heart disease, diabetes) or contraindicated medications (e.g. fentanyl, cyclosporine, pimozide, quinidine).

Statistical Considerations

Analyses will be conducted using IBM SPSS 24.0. Preliminary analyses of variance (ANOVAs) examine effects of sex and of medication order between phases. The primary outcome, number of days abstinent per assessment week (range of 0-5 days), will be analyzed using paired t-tests. Medication condition (active JNJ, placebo) is the within-subjects factor. Generalized estimating equations (GEE) assesses differences between conditions for the secondary outcome of withdrawal, limited to only responses from days in which smoking abstinence is confirmed. Results of cognitive testing are to be examined using paired t-tests for the CPT. Medication condition is a within-subjects factor. Similar to analyses of withdrawal, to detect potential efficacy of conditions on cognitive testing unconfounded by recent smoking, cognitive responses will be analyzed only when CO<10 on both the JNJ and placebo testing sessions, as in prior research (e.g. Perkins, Karelitz, *et al.* 2013b).

References

Brunzell DH, McIntosh JM (2012) Alpha7 nicotinic acetylcholine receptors modulate motivation to self-administer nicotine: Implications for smoking and schizophrenia. *Neuropsychopharmacol.* **37**:1134-1143.

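### The CPT paired t-test omits period in a CO-selected subset; a period-adjusted crossover analysis should lead

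*Combined protocol and SAP*

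**What the plan says.** The trial is a two-order crossover in 60 smokers. The CPT is a secondary outcome, given "on Mon of each quit week", that is, in weeks 3 and 6, so the second session repeats the same task.

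Four statements under Statistical Considerations bear on its analysis:

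- The test: "Results of cognitive testing are to be examined using paired t-tests for the CPT".
- The model: "Medication condition is a within-subjects factor". No period or sequence term is named.
- The analysis set: "cognitive responses will be analyzed only when CO<10 on both the JNJ and placebo testing sessions". The stated purpose is to keep recent smoking from confounding the comparison.
- The only provision for order: "Preliminary analyses of variance (ANOVAs) examine effects of sex and of medication order between phases". The text does not say which outcomes these ANOVAs cover, what model they use, or what follows if order matters.

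Under Random assignment, the plan uses permuted blocks and adds: "The same order assignment will not be repeated more than 3 consecutive times, to prevent an imbalance in the sequence of these orders". The primary analysis has the same form as the CPT test: "The primary outcome, number of days abstinent per assessment week (range of 0-5 days), will be analyzed using paired t-tests".

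**The concern.** In a two-period crossover, a change between periods that has nothing to do with drug enters the active-minus-placebo difference with a plus sign for those who take active second and a minus sign for those who take it first. Practice on a repeated attention task is an obvious candidate, although nothing in the documents shows that it occurs here.

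If the two orders are equally represented, the period effect cancels from the mean but remains in the variance, so the paired test loses power. If they are not, it also shifts the estimate.

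Blocking protects order balance among all those randomised. It does not protect balance in a subset chosen later, on treatment, by CO. The primary t-test also lacks a period term, but its stated analysis is not restricted to a CO-selected subset, so the loss of protected balance bears on the CPT and not on the primary.

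The preliminary ANOVAs could supply a period-adjusted drug effect if run as order by condition on the CPT subset. As written they do not say so, and the named CPT test stays unadjusted.

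**Working it through.** The plan gives no alpha, power, SD, effect size or expected subset size for the CPT, so there is no figure of its own to reproduce. From the documents come N = 60, two orders, permuted blocks, one CPT session per period and the CO<10 rule. Everything else below is an assumption, shown as a range.

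**Model.** Difference (active minus placebo) = d + s × π + e, with SD(e) = 1. Here s = +1 if active is second and −1 if first, and π is the practice (period) effect. Both d and π are in SDs of the within-person difference. The test is two-sided at 5%.

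**Estimators.** With n₁ participants taking active first and n₂ taking it second, n = n₁ + n₂:

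- Paired: mean of all differences; bias = π × (n₂ − n₁)/n; n − 1 df.
- Period-adjusted: half the sum of the two order-specific means; bias 0; SE = ½ × SD × √(1/n₁ + 1/n₂); n − 2 df. With complete pairs this equals the treatment effect from the crossover mixed model.

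**Subset size.** 60 × P(CO<10 on both Mondays), from a bivariate normal with correlation 0.3 to 0.7 between Mondays:

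| P(CO<10) on one Monday | Retained |
|---|---|
| 50% | 17.9–22.4 |
| 60% | 24.4–28.7 |
| 70% | 31.7–35.4 |
| 80% | 40.0–42.8 |

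The documents give no basis for choosing among these. I use n = 20, 29 and 41.

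**Order imbalance.** If the retained participants are a random draw from 30/30, the SD of (n₂ − n₁)/n is √[(60 − n)/(59n)]:

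- n = 20: √(40/1180) = 0.184
- n = 29: √(31/1711) = 0.135
- n = 41: √(19/2419) = 0.089

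These are the typical shifts of the paired estimate, as multiples of π. Particular splits, with the probability of one that uneven or worse:

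- 13/7: 0.17, shift 6/20 = 0.30π
- 19/10: 0.038, shift 9/29 = 0.31π
- 24/17: 0.09, shift 7/41 = 0.17π

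**Power, paired vs adjusted**, averaged over the random split (100,000 simulated trials per setting):

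| d | π | n = 20 | n = 29 | n = 41 |
|---|---|---|---|---|
| 0.6 | 0 | 0.72 vs 0.70 | 0.88 vs 0.87 | 0.96 vs 0.96 |
| 0.6 | 0.2 | 0.70 vs 0.70 | 0.87 vs 0.87 | 0.96 vs 0.96 |
| 0.6 | 0.3 | 0.69 vs 0.70 | 0.85 vs 0.87 | 0.95 vs 0.96 |
| 0.6 | 0.5 | 0.63 vs 0.70 | 0.81 vs 0.87 | 0.93 vs 0.96 |
| 0.6 | 0.75 | 0.53 vs 0.70 | 0.72 vs 0.87 | 0.88 vs 0.96 |
| 0.4 | 0.5 | 0.33 vs 0.39 | 0.46 vs 0.54 | 0.61 vs 0.70 |

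**Type I error.** Averaged over splits, the paired test is at about 0.05 with π = 0 and falls to 0.024–0.038 at π = 0.75, so it becomes conservative. The adjusted test stays at about 0.05. Given a fixed uneven split and π = 0.5, the paired test is at about 0.065 (13/7), 0.09 (19/10) and 0.07 (25/16); the adjusted test is again at about 0.05.

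**What a split does.** At 13/7 with π = 0.5 and d = 0.6, paired power is 0.39 or 0.84 depending only on which order is larger. Adjusted power is 0.68 either way.

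**Cost if there is no period effect.** 0 to 2 points of power on average. In a clearly uneven subset it is about 4 points: 0.72 vs 0.68 at 13/7, and 0.88 vs 0.84 at 19/10.

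**The case against.** The strongest case against is that no harm has been shown. No passage reports a period effect on the CPT. Up to 0.3 SD the adjusted test gains at most about 2 points at d = 0.6, and the notable losses need 0.5 SD or more. This stands, which is why the recommendation rests on the asymmetry between a small cost and a possible gain.

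The typical imbalance shift is also small. At π = 0.5 it is about 0.09, 0.07 and 0.04 SD, under half the standard error of the mean difference (1/√n = 0.22, 0.19, 0.16). The raised conditional type I errors at 19/10 and 25/16 belong to splits with probability 0.038 and 0.025; at 24/17 the figure is about 0.05. This stands too.

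The order ANOVAs open the analysis section before any outcome is named and may be meant to cover the CPT. Even so, no model or consequence is stated, so they do not put period into the CPT estimate.

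Period adjustment corrects for order, not for selection on CO. In one illustrative simulation in which drug made CO<10 easier to reach, the adjusted estimate was still biased by −0.20 CPT units, with type I error about 0.14. The CO<10 rule is a declared choice and is not disputed here, but the adjustment should not be presented as curing selection.

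Finally, the CPT is not alone. The primary t-test has no period term, and the withdrawal analysis is also confined to confirmed-abstinent days. A general statement on period terms would be reasonable.

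**Conclusion.** The concern holds. The stated CPT test has no period term, and it is applied to a subset in which order balance is not protected. If there is a period effect, the paired test treats it as noise and its estimate moves with the order imbalance. At d = 0.6 and n = 20 the loss is 7 to 8 points of power at a 0.5 SD effect and 17 to 18 points at 0.75 SD. At 0.2 SD or less the two tests are about equal.

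These figures assume a practice effect that is the same in both orders, normal errors, and a CO filter that thins the two orders at random. The effect size, practice effect and subset size are not in the documents. Average type I error is not inflated and the abstinence result is untouched. The change is worth making, with medium confidence, as an improvement to a secondary outcome; the omission does not invalidate the trial.

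**What to change.** Change the SAP wording as follows:

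1. Replace the CPT paired t-test with a crossover analysis containing treatment, period, sequence and a random participant effect.
2. Make it the lead CPT analysis whatever the preliminary order ANOVA shows, and state whether that ANOVA covers the CPT.
3. Report the number analysed in each order.
4. Keep CO<10 at both sessions as the lead rule.
5. Optionally, add a period-adjusted sensitivity analysis of all participants with both CPT sessions, to address selection after randomisation. It does not remove recent smoking, which is what the CO<10 rule is for, so it belongs beside the lead analysis and not in its place.

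No new data are needed. The statistical price is one degree of freedom, plus some precision when the subset is uneven.
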